12.6 AOM Relapse

AOM relapse will be defined as clinical success at the Day 12 visit and return for an interim/sick visit before Day 17 with AOM at that visit. Clinical success is defined as:

- no moderate to severe bulging of the TM, and
- no mild bulging of the TM with
 - o recent (less than 48 hours) onset of ear pain (otalgia), or
 - o intense erythema of the TM

Clinical success will be available in the eCRF and will not be programmatically derived. AOM relapse status will be shown in a listing.

Endpoints

AOM relapse will be a secondary endpoint and will be assessed using the subset of the mITT population that achieved clinical success at the Day 12 visit. Subjects in this subset who did not have an interim/sick visit before Day 17 at which AOM was diagnosed and who discontinued the study before Day 17 will be excluded from summaries and analyses.

Summaries and Analyses (see Section 13)

AOM relapse will be analyzed using logistic regression. A summary table will include frequencies and percentages of relapse and a p-value for the treatment group difference.

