All secondary efficacy endpoints will be evaluated in the safety population, without adjustment for multiplicity; therefore, p-values for these endpoints will be used only to aid in decision-making regarding whether any should be elevated in importance in future studies. These endpoints are:

- No MEE assessed at the Day 4 Visit and the Day 28 Visit by pneumatic otoscopy.
- No bulging of the TM assessed at the Day 12 Visit and the Day 28 Visit by pneumatic otoscopy.
- Normal tympanogram (Type A) assessed at the Day 4 Visit, the Day 12 Visit, and the Day 28 Visit by tympanometry.
- Complete or near complete resolution of symptoms (AOM cure), defined as an AOM-SOS score  $\leq 2$ , assessed at the Day 4 Visit, the Day 12 Visit, and the Day 28 Visit by in-clinic AOM-SOS score assessments.
- Change from baseline in AOM-SOS score over the planned 10-day treatment period by parent/caregiver diary data.
- At least a 50% reduction from baseline in the AOM-SOS score assessed at the Day 4 Visit, the Day 12 Visit, and the Day 28 Visit by in-clinic AOM-SOS score assessments.
- AOM treatment failure (clinical failure)\* at the Day 12 Visit.
- AOM relapse defined as those with clinical success# at the Day 12 Visit and who return for an interim/sick visit before Day 17 and have AOM.
- AOM recurrence defined as those with clinical success# at the Day 12 Visit and who return for an interim/sick visit from Day 17 through Day 28 and have AOM.

\*Treatment failure is defined as (1) moderate to severe bulging of the TM (Key Action Statement 1A), or (2) mild bulging of TM and recent (less than 48 hours) onset of ear pain (otalgia) (Key Action Statement 1B), or (3) mild bulging of the TM and intense erythema of the TM (Key Action Statement 1B).

#Clinical success for AOM relapse and AOM recurrence endpoints is defined as (1) no moderate to severe bulging of the TM (Key Action Statement 1A), and (2) no mild bulging of the TM

and no recent (less than 48 hours) onset of ear pain (otalgia) (Key Action Statement 1B), and (3) no mild bulging of the TM and no intense erythema of the TM (Key Action Statement 1B).

For the AOM cure endpoint, a sensitivity analysis will be done where AOM cure will be defined as AOM-SOS score = 0.

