Summaries and Analyses (see Section 13)

The 10-day mean AOM-SOS total score will be analyzed using a general linear model (GLM) with baseline AOM-SOS total score included as a covariate. A summary table will include means and SDs for each treatment group and a p-value for the difference.

AOM cure and AOM-SOS response will be summarized and analyzed separately by visit using logistic regression with baseline AOM-SOS total score included as a covariate. Summary tables will include frequencies and percentages of AOM cure and AOM-SOS response for each treatment group by visit and p-values for the differences.

12.5 **AOM Treatment Failure**

AOM treatment failure (clinical failure) will be defined as:

- moderate to severe bulging of the TM, or
- mild bulging of the TM with
 - o recent (less than 48 hours) onset of ear pain (otalgia), or
 - o intense erythema of the TM

AOM treatment failure (clinical failure) will be available in the eCRF and will not be programmatically derived. As a cross-check, a listing will be provided that shows degree of bulging TM, otalgia, and erythema in each ear and AOM treatment failure status at Day 12.

Confidential Page 25 of 35

Endpoints

AOM treatment failure (clinical failure) at the Day 12 visit will be a secondary endpoint.

Summaries and Analyses (see Section 13)

AOM treatment failure (clinical failure) will be analyzed using logistic regression. A summary table will include frequencies and percentages of treatment failure and a p-value for the treatment group difference.

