12.7 AOM Recurrence

AOM recurrence will be defined as clinical success at the Day 12 visit and return for an interim/sick visit Day 17 through Day 28 (including the Day 28 visit, which can be out-of-window) with AOM at that visit. Clinical success is defined as in Section 12.6.

AOM recurrence status will be shown in a listing.

Endpoints

AOM recurrence will be a secondary endpoint and will be assessed using the subset of the mITT population that achieved clinical success at the Day 12 visit. Subjects in this subset who did not have an interim/sick visit Day 17 through Day 28 at which AOM was diagnosed and who discontinued the study before Day 28 will be excluded from summaries and analyses.

Summaries and Analyses (see Section 13)

Confidential Page 26 of 35

AOM recurrence will be analyzed using logistic regression. A summary table will include frequencies and percentages of recurrence and a p-value for the treatment group difference.

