13.3 Missing Observations

For the primary efficacy analysis, multiple imputation will be used for missing observations with only treatment group included in the imputation model; ie, the observed within-treatment-group Bernoulli distribution of response will be the distribution from which random values are drawn to replace missing observations. The number of imputations will be the percentage of subjects with missing data, rounded up to an integer. Results from multiple imputations will be combined using the Rubin method.⁸ A complete-case sensitivity analysis will also be done, whereby for each endpoint only subjects with complete data are included. For secondary endpoints, only complete-case analyses will be done.

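### Relapse and recurrence are tested only among Day 12 successes, a subset that treatment can change, so the comparison can mislead about an effective drug

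*SAP*

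**What the plan says.** SAP 12.6 states that AOM relapse "will be assessed using the subset of the mITT population that achieved clinical success at the Day 12 visit". It is analysed by logistic regression, and the output is specified: "A summary table will include frequencies and percentages of relapse and a p-value for the treatment group difference". SAP 12.7 sets up recurrence (Day 17 through Day 28) in the same way and on the same subset.

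Both sections have a rule for children who leave early. For relapse, those with no AOM diagnosed at an interim visit before Day 17 and "who discontinued the study before Day 17 will be excluded from summaries and analyses". For recurrence, those with no AOM diagnosed from Day 17 through Day 28 and "who discontinued the study before Day 28 will be excluded from summaries and analyses". A child who leaves early after a diagnosed event stays in. SAP 12.7 has no rule for a child who relapsed before Day 17, so that child remains in the recurrence denominator.

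SAP 13.3 adds: "For secondary endpoints, only complete-case analyses will be done".

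The conditioning starts in Protocol 9.4.1: "AOM relapse defined as those with clinical success# at the Day 12 Visit and who return for an interim/sick visit before Day 17". On population, the protocol says: "All secondary efficacy endpoints will be evaluated in the safety population, without adjustment for multiplicity". SAP 12.5 makes Day 12 failure a tested outcome in its own right: "AOM treatment failure (clinical failure) at the Day 12 visit will be a secondary endpoint".

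**The concern.** Day 12 success is observed after randomisation and may depend on treatment. If the drug works, its success group contains children who would have failed on placebo, and these may be the harder cases. The two success groups are then different kinds of children. The SAP 13.1 covariates (age group, daycare attendance and, where applicable, a baseline value) cannot be relied on to make them comparable.

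The leaver rule depends on the outcome: an early exit counts if AOM was seen and is removed if not. The relapse and recurrence windows also interact, because a relapser who reaches Day 28 without a further AOM diagnosis is scored as having no recurrence.

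Fewer later episodes of AOM is part of the objective in Protocol 9.1, and SAP 2.2 names relapse and recurrence rates as measures of maintained resolution. Protocol 9.4.1 says that the secondary p-values are to help decide which endpoints are elevated in future studies. A comparison that can change sign serves that purpose poorly.

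**Working it through.** **Inputs.** The documents give no rate, power or sample size for relapse or recurrence, so there is no plan figure to reproduce for these endpoints. The SAP's 93% power concerns the primary family. It reproduces as 93.3% (63 per arm, 0.40 vs 0.65 and 0.30 vs 0.55, Hochberg, independent endpoints) and this point does not affect it. The documents supply 70 per arm and whole-study dropout of 10% (SAP 5) or 12% (Protocol 9.2). All success and relapse rates below are assumptions.

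**1. Selection into the subset.** Assume Day 12 success of 60% on placebo and 80% on drug. Relapse risk is 10% in children who succeed on either arm and r in the further 20% who succeed only on drug.

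- Subset rate on drug = (0.60 × 0.10 + 0.20 × r) / 0.80. On placebo it is 10.0%.
- r = 0.30: (0.06 + 0.06) / 0.80 = 15.0% vs 10.0%.
- If the drug also cuts every child's relapse risk by a fifth: 0.8 × 15.0% = 12.0% vs 10.0%. It still looks worse.
- Range: r = 0.10 gives 10.0% (no distortion); r = 0.40 gives 17.5%.
- With the one-fifth cut, the subset rates are equal at r = 0.20: 0.8 × (0.06 + 0.04) / 0.80 = 10.0%. The drug looks worse only above that.

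Failure at Day 12 or later AOM, among all children:

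- r = 0.30, no effect on relapse: drug 0.20 + 0.80 × 0.15 = 32.0%; placebo 0.40 + 0.60 × 0.10 = 46.0%.
- With the one-fifth cut: drug 0.20 + 0.80 × 0.12 = 29.6%; placebo 46.0%.

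Widening the relapse denominator to all children does not cure this. With an equal 10% risk, relapse would be 0.60 × 0.10 = 6% on placebo and 0.80 × 0.10 = 8% on drug, because more children on drug are at risk of relapsing.

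**2. The leaver rule.** Let p be the true risk and d the share leaving during the window, with event and exit times uniform and independent. Observed events are E = p(1 − d/2), event-free completers are N = (1 − p)(1 − d), and the reported rate is E / (E + N).

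- p = 0.15, d = 0.10: 0.1425 / (0.1425 + 0.765) = 15.7%, or +0.7 points.
- p = 0.20, d = 0.12: 0.188 / (0.188 + 0.704) = 21.1%, or +1.1 points.
- For p from 5% to 30% at d = 10–12%, the bias is +0.3 to +1.4 points.
- Equal true risk of 15% with dropout of 5% vs 12%: 15.3% vs 15.9%, a false difference of about 0.5 points.

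If exit is related to outcome, the sign depends on the leavers. Suppose 15% is observed and 10% are excluded:

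- Leaver risk 30%: true rate 0.9 × 0.15 + 0.1 × 0.30 = 16.5%, so the report is 1.5 points too low.
- Leaver risk 50%: true rate 0.135 + 0.05 = 18.5%, so it is 3.5 points too low.
- Leaver risk 15%: no bias.

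**3. Relapsers in the recurrence denominator.** Assume 100 successes per arm, 20 relapses in arm A and 5 in arm B, and later AOM in 20% of non-relapsers and 5% of relapsers.

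- Recurrence, A: (80 × 0.20 + 20 × 0.05) / 100 = 17.0%.
- Recurrence, B: (95 × 0.20 + 5 × 0.05) / 100 = 19.25%.
- Any AOM after Day 12: A 20 + 16 = 36%; B 5 + 19 = 24%.

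The arm with four times the relapses shows less recurrence. If relapsers had the same 20% later risk, both arms would read 20%, and the difference in relapse would simply not show.

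**The case against.** Relapse presupposes an earlier success, and the protocol defines both endpoints that way, so the conditioning is not something the SAP introduced. The endpoints are secondary and unadjusted, and no efficacy conclusion rests on them.

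The plan also has comparisons that avoid this subset: Day 12 treatment failure (SAP 12.5), no bulging and no MEE at Day 28, and sensitivity analyses requiring no recurrence of bulging or of MEE for the rest of the study (SAP 12.1, 12.2). Failure, relapse and recurrence share one table (14.2.7.1), so a reader would see the Day 12 difference beside the later rates.

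The reversal rests on assumed rates and would rarely be decisive. At 15.0% of 56 against 10.0% of 42, the pooled standard error is 0.068, z = 0.05 / 0.068 = 0.73 and p is about 0.46. The all-children comparison of 32.0% vs 46.0% with 70 per arm has a standard error of 0.082, z = 1.70, p about 0.09, and roughly 40% power.

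All of this stands, and it limits the weight of the point. It does not remove it. None of the existing analyses combines Day 12 clinical success with freedom from later AOM, the sensitivity analyses are complete-case at Day 28, and the relapse and recurrence p-values would still be read as treatment comparisons.

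A reader might infer that the leaver rule inflates the rates as a matter of course. The documents do not support that: they say nothing about the risk of leavers, and the sign turns on it. Nor do they support extrapolating to heavy dropout. They assume 10% or 12% over the whole study, and for relapse only exits between the Day 12 visit and Day 17 count.

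**Conclusion.** The concern holds in a limited form. The planned relapse and recurrence p-values compare groups selected after randomisation by an outcome that treatment may change, and the comparison can point against an effective drug. In the base case the subset rate on drug runs from 10.0% to 17.5% against 10.0% on placebo as the assumed risk in drug-only successes goes from 10% to 40%. The size depends wholly on those assumptions, and the distortion is nil if these children carry ordinary risk. It would be too strong to say that the plan will make a working drug look worse.

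The leaver rule matters less: about 1 point upward at 10–12% dropout if exit is unrelated to outcome, downward if leavers are at higher risk, and no planned sensitivity analysis for these endpoints would show which. Scoring relapsers as free of recurrence follows from the text of SAP 12.7; whether it changes the comparison depends on their later risk.

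This is a worthwhile improvement to secondary endpoints. It does not threaten the primary analysis.

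**What to change.** Add one tested comparison in all mITT children: clinical success at Day 12 and no AOM at any later visit through Day 28 (yes/no), counting the Day 28 visit as SAP 12.7 already does.

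- Count Day 12 failure, or any observed later AOM, as non-response.
- Where Day 12 status is missing, or a child exits before Day 28 without AOM, multiply impute by treatment group as in SAP 13.3. Do not exclude these children or treat them as AOM-free. Report how many there are, since the imputation assumes that leavers resemble the observed children in their arm.
- Report relapse and recurrence among Day 12 successes as descriptive rates without treatment p-values, and show relapsers separately in the recurrence summary.
- List the change in SAP Section 16, which at present records the move to complete-case mITT but not the restriction to Day 12 successes.

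The cost is a few lines of SAP text and one derived variable from data already collected. The small downside is that the tested endpoint differs from the protocol's relapse and recurrence wording.

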12.7 AOM Recurrence

AOM recurrence will be defined as clinical success at the Day 12 visit and return for an interim/sick visit Day 17 through Day 28 (including the Day 28 visit, which can be out-of-window) with AOM at that visit. Clinical success is defined as in Section 12.6.

AOM recurrence status will be shown in a listing.

Endpoints

AOM recurrence will be a secondary endpoint and will be assessed using the subset of the mITT population that achieved clinical success at the Day 12 visit. Subjects in this subset who did not have an interim/sick visit Day 17 through Day 28 at which AOM was diagnosed and who discontinued the study before Day 28 will be excluded from summaries and analyses.

Summaries and Analyses (see Section 13)

Confidential Page 26 of 35

AOM recurrence will be analyzed using logistic regression. A summary table will include frequencies and percentages of recurrence and a p-value for the treatment group difference.

13. STATISTICAL METHODS

13.1 Logistic Regression

Logistic regression models will include treatment group as a main effect and the randomization stratifiers (age group, daycare attendance) and an appropriate baseline value (if applicable) as covariates. Model-based LS means and SEs will be reported for each treatment group, along with a p-value for the treatment group comparison. For sparse data, two-sided Fisher's exact tests will be used (ie, with no covariate adjustment).

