5. SAMPLE SIZE AND POWER

The power calculation is based on a 2-sided Pearson chi square test of each of the two endpoints in the primary efficacy endpoint family and control of type 1 error using the step-up Hochberg procedure.⁸ The minimally important difference in proportions for both endpoints is approximately 0.25. With 70 subjects randomized per treatment group, an assumed dropout rate of 10%, and using multiple imputation as described in Section 13.3, this study will have 93% power to detect a treatment effect in at least one of the two endpoints assuming 40% of placebotreated subjects will have no bulging TM at Day 4 and 30% of placebotreated subjects will have no MEE at Day 12. A summary of sample size requirements is as follows:

Total N	Power
100	82%
102	82%
120	88%
132	91%
140	93%

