8.4 Subgroups

Summary statistics for the primary efficacy endpoint family will be provided for the following subgroups:

- Male, female
- White, non-white
- Unilateral, bilateral disease at baseline
- History, no history of recurrent AOM, defined as 3 or more episodes in the preceding 6 months or 4 or more episodes over the course of 12 months
- Age stratum (\geq 6 to <12 months, \geq 12 to \leq 24 months)
- Daycare attendance stratum (exposed, not exposed to 3 or more children outside of the home for 10 or more hours per week)
- Study site

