11.4 Ear Examination

Examination of each ear will be done at each study visit. Summaries, by ear and visit, will be done for: TM findings (intact, perforated,), color (gray, pink, pale yellow, white, amber, blue), translucency (translucent, semi-opaque, opaque), mobility (none, 1+, 2+, 3+, 4+), air fluid interface (yes, no), otalgia (yes, no), distinct erythema (yes, no), position of the TM (neutral, retracted, 1+ bulging, 2+ bulging, 3+ bulging), otorrhea (no, serous, purulent), and diagnosis (no effusion, OME, AOM).

Confidential Page 21 of 35

Shift tables will summarize changes from baseline in normal/abnormal status, where "abnormal" will be limited to "definitely abnormal" defined as follows:

• TM findings: perforated

• Color: pale yellow, white, amber, blue

• Translucency: semi-opaque or opaque

• Mobility: none

• Air fluid interface: yes

• Otalgia: yes

• Distinct erythema: yes

• Position of TM: retracted, 1+ bulging, 2+ bulging, 3+ bulging

• Otorrhea: serous, purulent

Diagnosis: AOM, OME

Parameters will be summarized within treatment group for (a) first or only affected ear and (b) second or non-affected ear. Since either one ear or both ears can have AOM at baseline, this approach will allow descriptive comparisons between OP0201 and placebo treatment groups on number of affected ears (ie, one or both ears) and shifts from baseline, by visit, for both affected and non-affected ears at baseline.

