13.4 Multiplicity

The familywise type 1 error rate for the primary efficacy endpoint family will be 0.05 and will be controlled using the Hochberg procedure. Specifically, the p-value of the endpoint with the highest p-value will be compared against the 0.05 significance level and, if significant, both endpoints will be declared significant; if the endpoint with the highest p-value is not significant at the 0.05 level, the other endpoint will be tested at the 0.025 significance level. A positive treatment effect on efficacy will be concluded if at least one of the two endpoints is significant.

Confidential Page 27 of 35

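### The primary logistic models leave out disease laterality, a recorded baseline factor that is plausibly prognostic; adding it would be a modest, nearly free gain in power

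*SAP*

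**What the plan says.** **Covariates.** SAP 13.1: "Logistic regression models will include treatment group as a main effect and the randomization stratifiers (age group, daycare attendance". The sentence then allows for a suitable baseline value if there is one. SAP 12.4 names that value for the symptom endpoints (baseline AOM-SOS), but SAP 12.1 and 12.2 name none for the two primary endpoints. Protocol 9.4.1 lists the two stratifiers and degree of bulging at baseline. SAP section 16 does not record the missing bulging term as a change from the Protocol.

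**Laterality.** SAP 8.4 lists "Unilateral, bilateral disease at baseline" among the subgroups for the primary endpoint family, as does Protocol 9.4.1, and SAP Appendix B has a by-laterality table for each primary endpoint. SAP 11.4 notes: "Since either one ear or both ears can have AOM at baseline". Randomization is stratified by daycare and age only (Protocol 6.3, SAP 6.1).

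**Unit of analysis.** The hypotheses in Protocol 9.1 concern proportions of participants. SAP 12.1 and 12.2 have each ear examined separately and give no rule for combining two ears into one result. The rationale in Protocol 1.1 and 2.1 writes the tympanic membrane with an optional plural, which points to both ears being clear. The only explicit combining rule in the SAP is for the tympanogram (SAP 12.3), where a normal result in either ear counts.

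**Power.** SAP 5: "The power calculation is based on a 2-sided Pearson chi square test of each of the two endpoints". "The minimally important difference in proportions for both endpoints is approximately 0.25". The placebo rates are set by "assuming 40% of placebotreated subjects will have no bulging TM at Day 4" and "30% of placebotreated subjects will have no MEE at Day 12". Stated power is 93% for at least one endpoint, with 70 per arm and 10% dropout.

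**The concern.** If a child must be clear in both ears, a child with two diseased ears has two chances to fail. Laterality would then predict the outcome, and degree of bulging would not fully stand in for it, because grade and number of ears are different things. In a logistic model, adjusting for a prognostic baseline factor moves the treatment log odds ratio further from zero by more than it inflates the standard error, so power rises. It also removes the effect of a chance difference between arms in the bilateral share, which stratification does not control here.

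At stake is some unused power and precision. The validity of the test is not at issue. The naming gap matters for a second reason: with the baseline value left open for both primary endpoints, the primary model is not fully fixed in advance.

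**Working it through.** **1. Reproduce the plan's power (SAP 5).** Inputs: rates 0.40 vs 0.65 (Day 4) and 0.30 vs 0.55 (Day 12), from the placebo rates plus 0.25; n = 70 × 0.90 = 63 per arm; two-sided test. SAP 13.4: "The familywise type 1 error rate for the primary efficacy endpoint family will be 0.05 and will be controlled using the Hochberg procedure".

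Power of one test = Φ{[Δ√n − z√(2p̄q̄)] / √(p₁q₁ + p₂q₂)}.

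- Day 4 at 0.05: [0.25 × 7.937 − 1.960 × 0.7062] / 0.6837 = 0.878, power 81.0%; at 0.025, 72.1%.
- Day 12 at 0.05: [0.25 × 7.937 − 1.960 × 0.6991] / 0.6764 = 0.908, power 81.8%; at 0.025, 73.1%.
- Hochberg, endpoints taken as independent: 1 − (1 − 0.721)(1 − 0.731) + (0.810 − 0.721)(0.818 − 0.731) = 93.3%.

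This matches the stated 93%. The calculation contains no covariates.

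**2. How strong could laterality be?** The documents do not say. Assume 50% bilateral and a both-ears rule. If ears clear independently with probability q, the placebo rate is (q + q²)/2.

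- Day 4: (q + q²)/2 = 0.40 gives q = 0.525 and q² = 0.275, odds ratio (0.525/0.475)/(0.275/0.725) ≈ 2.9.
- Day 12: (q + q²)/2 = 0.30 gives q = 0.422 and q² = 0.178, odds ratio ≈ 3.4.
- If the two ears of a child always agree, the odds ratio is 1.

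This mechanism therefore supports odds ratios from 1 to about 3.

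**3. Power with and without laterality.** Simulation: 10,000 trials per scenario, 63 per arm, logit(response) = a₀ + (a₁ − a₀) × treatment − ln(OR) × bilateral, with a₀ and a₁ solved so that the overall rates stay at those in step 1. Wald test of treatment. Entries are power without → with laterality.

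At least one endpoint under Hochberg:

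| Odds ratio | 30% bilateral | 50% bilateral | 60% bilateral |
|---|---|---|---|
| 1 | 93.6 → 93.3 | 93.3 → 93.2 | 93.0 → 92.9 |
| 1.5 | 93.2 → 93.4 | 93.3 → 93.5 | 93.2 → 93.5 |
| 2 | 92.7 → 93.3 | 92.9 → 93.7 | 93.1 → 94.0 |
| 3 | 92.6 → 94.3 | 92.2 → 94.4 | 92.5 → 94.4 |
| 5 | 92.6 → 95.9 | 91.6 → 95.9 | 92.0 → 95.6 |

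Single endpoints at 0.05, 50% bilateral:

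| Odds ratio | Day 4, no bulging | Day 12, no MEE |
|---|---|---|
| 1 | 80.5 → 81.2 | 82.1 → 81.8 |
| 2 | 80.3 → 82.5 | 81.9 → 82.5 |
| 3 | 79.3 → 83.1 | 81.8 → 83.8 |
| 5 | 79.9 → 86.1 | 82.3 → 86.8 |

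Simulation error is about 0.3 points for the family figure and 0.4 for single endpoints. The odds ratio of 5 needs more than step 2 supplies: at 50% bilateral it implies placebo rates of 58% and 22% at Day 4, while independent ears would give 0.58² = 34% in bilateral children.

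Limits: age, daycare and baseline bulging were left out of both models; imputation was approximated by the 63 observed per arm; the two endpoints are correlated only through laterality.

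**4. Chance imbalance.** With 70 per arm and 50% bilateral (assumed), the standard deviation of the between-arm difference in bilateral share is √(2 × 0.25/70) = 8.5 points. A difference above 10 points occurs in about 24% of trials, and above 15 points in about 8%. With the 25-point outcome gap of step 2 (0.525 vs 0.275), a 10-point imbalance shifts the unadjusted difference by 0.10 × 25 = 2.5 points, against a target of 25.

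**The case against.** The strongest reply is that the mechanism is inferred. No passage says that both ears must clear, and the one combining rule the SAP does give (tympanogram, either ear) would weaken or reverse the association if applied here. For MEE the link is looser still: SAP 11.4 allows OME as a diagnosis for an ear, so the ear without AOM may also hold fluid, and AOM laterality is not a count of ears at risk. Both points stand, and they are why the ear-to-child rule belongs in the fix.

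A reader might infer that laterality is a strong predictor and that substantial power is being given away. The documents contain no figure for either. The larger single-endpoint gains of 4 to 6 points arise only at an odds ratio of 5, and success in this trial is judged on at least one of two endpoints, where the gain is smaller. A reader might also infer that the 93% is wrong. It is not: it rests on an unadjusted test, and simulated power without laterality stays at about 92% to 94% for odds ratios up to 3.

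It is also fair to say that the comparison in the working is with a treatment-only model. If baseline bulging is already in the model and is related to laterality, the added gain would probably be smaller. Chance imbalance is possible rather than likely, does not invalidate a randomized test, and would be visible in the planned laterality tables. Finally, covariate choice in an exploratory Phase 2a study is partly judgement. What remains is that the term is available, costs almost nothing, and the primary model needs its covariates named in any case.

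**Conclusion.** The point holds as a modest efficiency improvement, not as an error. Laterality is recorded, is already a subgroup for both primary endpoints, is not a stratifier, and is missing from the covariates in both documents. Under a both-ears rule it is plausibly prognostic. With 63 per arm and 30% to 60% bilateral (assumed), adjustment is worth about 0 to 1 point of power for at least one endpoint at odds ratios up to 2, about 2 points at 3, and 3 to 4 points at 5. For a single endpoint it is worth about 0 to 4 points at odds ratios up to 3. These figures rest on an assumed bilateral share, an assumed strength of association, and a comparison model without other covariates. The more basic gaps are the unnamed baseline covariate and the unstated rule for combining ears.

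**What to change.** Before unblinding, amend SAP 13.1 to name the covariates for both primary endpoints: age stratum, daycare stratum, worst-ear baseline degree of bulging, and laterality (unilateral/bilateral). State in SAP 12.1 and 12.2 how two ears become one child-level response, including how an ear without AOM at baseline counts towards the MEE endpoint. Because the imputation model in SAP 13.3 contains treatment group only, add laterality there too, so that imputed values do not dilute its association with outcome.

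The laterality term costs one parameter in about 137 children (140 less the 3 excluded from the mITT population). No new data are needed. If laterality turns out not to be prognostic, the loss is negligible: at an odds ratio of 1 and 50% bilateral, family power is 93.3% without the term and 93.2% with it.
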